## **7.2. Number of Subjects**

A total of 24 evaluable subjects will be enrolled to the study (12 male and 12 female) at approximately 3 investigational centers.

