### **8.3. Subject Withdrawal Criteria**

Subjects will be informed that they are free to withdraw from the study at any time and for any reason. The investigator may remove a subject from the study if, in the investigator's opinion, it is not in the best interest of the subject to continue the study. Examples of other reasons subjects may be discontinued from the study are: a change in compliance with an inclusion or exclusion criteria, occurrence of AEs, occurrence of pregnancy, use of a prohibited therapy or subject is unwilling or refuses to continue with the protocol defined procedures, treatments and/or study visits and/or subject withdraws consent.

Subjects will be permanently discontinued from the study in the event of any of the following:

- Severe infection requiring parental antimicrobial therapy or hospitalization
- Symptomatic herpes zoster
- Malignancy – except for non-melanoma skin cancer (SCC or BCC) not in or near the treatment area
- Anaphylactic or severe allergic reaction
- WBC Count: < 1 x 10^9/L or second occurrence of < 2 x 10^9/L
- ANC:<0.5 x 10^9/L or second occurrence of < 1 x 10^9/L
- Lymphocyte count: < 0.3 x 10^9/L or second occurrence of < 0.5 x 10^9/L
- Platelet count: < 50 x 10^9/L or second event of < 75 x 10^9/L - in each case, value should be confirmed by retesting before treatment discontinuation
- Hemoglobin: < 6.5 g/dL or second occurrence of < 8 g/dL - in each case, value should be confirmed by retesting before treatment discontinuation
- AST or ALT:
  - > 5 x ULN persisting for 2-weeks of study medication interruption or second event of > 5 x ULN
  - 3 x ULN with total bilirubin >2 x ULN or symptoms of hepatocellular injury (fatigue, nausea, vomiting, right upper quadrant pain or tenderness, fever, rash and/ or eosinophilia (>5%).
- Any subject who develops any of the following ECG findings during the active treatment phase will be instructed to stop study medication and will be withdrawn from the study:
  - Clinically significant rhythm disturbance other than sinus rhythm or ectopic supraventricular rhythm (ectopic atrial rhythm)
  - Clinically significant conduction disturbance including PR >240msec, pre-excitation (delta wave and PR <120msec), second degree or higher AV block

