- New finding of QRS>120ms (if not present at screen. For example, subjects with Right Bundle Branch Block at screening would not need to be withdrawn from the study if their subsequent ECGs remained unchanged).
- Evidence of QT-interval prolongation, defined as an increase in the QTcF interval>60ms from Visit 1
- Acute signs of ischemia or infarction
- Any ECG abnormality which may, in the opinion of the investigator, represent a new medical issue of concern

A subject that experiences any of the above events must be discontinued from study medication treatment, the site staff must inform the Aclaris medical monitor of the event, and the site staff must perform protocol-required procedures for trial discontinuation and follow-up.

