## **13. STATISTICS**

### **13.1. Statistical Methods**

Summary descriptive statistics (N, mean, median, SD) by visit will be provided for all safety and efficacy parameters. The Intent to Treat population will be used for all efficacy assessments and the Safety population will be used for all safety assessments. No data imputation will be used. Primary and secondary efficacy parameters are described in the sections below.

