	(Min, Max)	(xxx,xxx)	(xxx,xxx)	(xxx,xxx)	(xxx,xxx)	(xxx, xxx)	(xxx, xxx)	
V14 –Week 44	n	XX	XX	XX	XX	XX	XX	
	Mean (SD)	xx.x (xx.xx)						
	Median	xxx.x	xxx.x	xxx.x	xxx.x	xxx.x	xxx.x	
	(Min, Max)	(xxx,xxx)	(xxx,xxx)	(xxx,xxx)	(xxx,xxx)	(xxx,xxx)	(xxx,xxx)	

^a Baseline is selected as the last measurement prior to the first application of study medication.

^b Includes early terminations or follow-ups collected during the first 26 weeks or during the additional six months for patients opting to continue treatment in the optional six month extension.

23 Apr 2019 Statistical Analysis Plan

Table 14.3.2.1
Vital Signs: Systolic Blood Pressure (mmHg)
Safety Population

		Fe	Female		Male		tal
Visit	Statistic	Value	Change	Value	Change	Value	Change
V15 – Week 48	n	XX	XX	XX	XX	XX	XX
	Mean (SD)	xx.x (xx.xx)					
	Median	XXX.X	XXX.X	XXX.X	XXX.X	XXX.X	XXX.X
	(Min, Max)	(xxx,xxx)	(xxx,xxx)	(xxx,xxx)	(xxx,xxx)	(xxx,xxx)	(xxx, xxx)
V16 – Week 52	n	xx	XX	XX	XX	XX	XX
	Mean (SD)	xx.x (xx.xx)					
	Median	XXX.X	XXX.X	XXX.X	XXX.X	XXX.X	XXX.X
	(Min, Max)	(xxx, xxx)	(xxx,xxx)	(xxx,xxx)	(xxx,xxx)	(xxx, xxx)	(xxx, xxx)
FU/Early Termination ^b	n	XX	XX	XX	XX	XX	XX
v	Mean (SD)	xx.x (xx.xx)					
	Median	xxx.x	xxx.x	xxx.x	xxx.x	xxx.x	xxx.x
	(Min, Max)	(xxx, xxx)	(xxx,xxx)	(xxx,xxx)	(xxx, xxx)	(xxx, xxx)	(xxx,xxx)

^a Baseline is selected as the last measurement prior to the first application of study medication.

^b Includes early terminations or follow-ups collected during the first 26 weeks or during the additional six months for patients opting to continue treatment in the optional six month extension.

Aclaris Therapeutics Inc. 23 Apr 2019
Protocol: ATI-50002-AGA-201 Statistical Analysis Plan

PROGRAMMING NOTE: to be repeated for the following:

Table 14.3.2.2	Vital Signs	Diastolic Blood Pressure	(mmHg) Safety Population
1 adic 14.5.4.4	vitai bigiis.	Diastone Dioou i ressure	(miming) Saicty i opulation

Table 14.3.2.3 Vital Signs: Heart Rate (bpm) Safety Population
Table 14.3.2.4 Vital Signs: Respiratory Rate (bpm) Safety Population
Table 14.3.2.5 Vital Signs: Temperature (Degrees C) Safety Population

23 Apr 2019 Statistical Analysis Plan

Table 14.3.3
ECG Interpretation: Shift from Baseline to Worst Assessment Post Baseline
Safety Population

Group	Worst Post-Baseline Interpretation, n (%)								
Baseline Interpretation	Normal	Abnormal, NCS	Abnormal, CS	Missing	Total				
Female (Na=xx)									
Normal	xx(xx.x)	xx (xx.x)	xx(xx.x)	xx (xx.x)	xx (xx.x)				

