>1.5xULN Alk Phos	x(x.x)	x(x.x)	x(x.x)
Elevation of AT ^b and Bilirubin			
>3xULN AT and >1.5xULN Bilirubin	x(x.x)	x(x.x)	x(x.x)
>3xULN AT and >2xULN Bilirubin	x(x.x)	x(x.x)	x(x.x)
>3xULN AT and >=2xULN Bilirubin and Alkaline Phosphatase <2xULN or missing	x(x.x)	x(x.x)	x(x.x)

^a Patients with both ALT and AST abnormalities for the same lab draw (same date and time) are counted as one event.

PROGRAMMING NOTE: It is intentional that the last criterion has '=' added to the bilirubin threshold – to match exactly FDA Guidance doc

[figure not shown]
^b AT = aminotransferase. Either AST or ALT (or both) elevated.

23 Apr 2019 Statistical Analysis Plan

Table 14.3.6 Number and Percent of Patients Meeting Laboratory Criteria for Potential Renal Impairment Safety Population

Criteria	Female (N=xx) n (%)	Male (N=xx) n (%)	Total (N=xx) n (%)	
Change from Baseline ≥ 0.5 mg/dL	x (x.x)	x (x.x)	x (x.x)	
>1.5xULN Creatinine	x(x.x)	x(x.x)	x(x.x)	
EITHER Change from Baseline >=0.5 mg/dL or >1.5xULN Creatinine	x(x.x)	x(x.x)	x(x.x)	
BOTH Change from Baseline >= 0.5 mg/dL and >1.5xULN Creatinine	x(x.x)	x(x.x)	x(x.x)	

Figure 14.1
Association of Selected Efficacy Measures with Fit Linear Regression Line
ITT Population: Visit = V5 Week 8

Reperat for:

Figure 14.2	Association of Selected Efficacy Measures with Fit Linear Regression Line, ITT Population: Visit=V7 Week 16
Figure 14.3	Association of Selected Efficacy Measures with Fit Linear Regression Line, ITT Population: Visit=V10 Week 26
Figure 14.4	Association of Selected Efficacy Measures with Fit Linear Regression Line, ITT Population: Visit=V16 Week 52

For the following plot change in averge hair wdth (vertical) vs Investigaor Global Assessment [4 figures – All timepoints on page]. Indicate timepoint at top of each of the visits. Separate color for males and females and linear regression line as per figure 14.1.Add Foonote: Note Lines represent fit linear regression line.

Figure 14.5 Association of Change in Nonvellus Target Area Average Hair Width with Investigator Global Assessment, ITT Population

For the following plot change in averge hair wdth (vertical) vs Subject Self Assessment [4 figures – All timepoints on page] Indicate timepoint at top of each of the visits. Separate color for males and females and linear regression line as per figure 14.1.Add Foonote: Note Lines represent fit linear regression line.

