Appendix 16.2.3.8 Electrocardiogram – Evaluator Interpretation

Group: Female, Male

Patient	Visit	Study Day ^a	Interpretation ^b	Specify – if abnormal
XX-XXX		XX	Normal	
		XX	Abnormal, CS	Sinus Bradycardia
		XX	Abnormal, NCS	Inverted T Waves; T Wave Abnormality: Biphasic T Waves
		XX	Abnormal, NCS	

Programming Note: Suggestion is to list all abnormalities at a given collection be listed according to "interpretation" (ie CS and/or NCS). So if there are multiple reasons, as in the hypothetical example above for NCS, separate them by semi-colons.

^a Assessment Date – Date of First Application (+1 if ≥ first application of study medication).

^b CS = Clinically Significant; NCS = Not Clinically Significant

23 Apr 2019 Statistical Analysis Plan

Protocol: ATI-50002-AGA-201

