Appendix 16.2.3.9 Clinical Laboratory Assessments: Hematology

Group: Female, Male

Patient	Age (years)	Gender	Parameter (unit)	Visit	Study Day ^a	Value	Normal Range		List Criteria Met, if applicable, for Hold of Study Medication
xx-xxx	60	Female	Hemoglobin (g/dL)		-10 -1 ^b 28 38	XXX XXX XXX XXX	XX.X-XX.X	L H	< 8 g/dL or decrease > 2 g/dL
			Hematocrit (%)						

^a Assessment Date – Date of First Application (+1 if ≥ first application of study medication).

PROGRAMMING NOTE: Sort by group, patient, parameter, and study day. For criteria for holding study medication see protocol – Section 10.2.4.1

	Repeat format for:
Appendix 16.2.3.10	Clinical Laboratory Assessments: Biochemistry
Appendix 16.2.3.11	Clinical Laboratory Assessments: Hormones

^b Value used for baseline.

23 Apr 2019 Statistical Analysis Plan

Protocol: ATI-50002-AGA-201

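### The SAP plans no ECG interval output, so the protocol's QTcF, QRS and PR withdrawal limits cannot be checked independently of what sites flagged

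*SAP*

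**What the plan says.** **Withdrawal limits.** Protocol 8.3 lists ECG findings that end participation. One is "Evidence of QT-interval prolongation, defined as an increase in the" QTcF interval of more than 60 ms from Visit 1. Another is a QRS above 120 ms that was not present at screening. A third is "Clinically significant conduction disturbance including PR >240msec", along with pre-excitation and higher-degree AV block.

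**Reporting commitment.** Protocol 13.1 states: "Summary descriptive statistics (N, mean, median, SD) by visit will be provided for all safety and efficacy parameters". Protocol 13.4 adds that ECG results will be tabulated. Safety is part of the primary objective (6.1).

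**How ECGs are read.** Under protocol 12.1.4 a central cardiology laboratory processes the tracings. An evaluator calls each one normal or abnormal, and the investigator comments on the clinical relevance of abnormal ones.

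**SAP ECG output.** The table list has one entry, Table 14.3.3, "ECG Interpretation: Shift from Baseline to Worst Assessment Post Baseline". Its categories are normal, abnormal not clinically significant, abnormal clinically significant, and missing. The listing index has one entry, Appendix 16.2.3.8, "Electrocardiogram – Evaluator Interpretation", with a free-text field for abnormal tracings.

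**Laboratory holds.** Table 4 in protocol 9.9 has seven rows: WBC, ANC, lymphocytes, platelets, hemoglobin, AST/ALT and creatinine. SAP Table 14.3.5 counts AST/ALT at several multiples of ULN. Table 14.3.6 counts creatinine at ">1.5xULN Creatinine" and at a rise of 0.5 mg/dL or more. Listing 16.2.3.9 (hematology) has a column for the hold criterion met, and the format is repeated for biochemistry in 16.2.3.10. Its programming note reads: "For criteria for holding study medication see protocol – Section 10.2.4.1".

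**The concern.** The QTcF rule concerns a within-subject change against the Visit 1 tracing. A label of normal or abnormal on a single tracing does not carry that information, and protocol 12.1.4 gives the evaluator no QTcF-change criterion. If a site does not compute the change, or computes it and does not act, nothing in the planned output would show it.

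The adverse event and disposition listings record only cases that someone had already noticed. They can show that a withdrawal happened, but not that one was missed. The stake is the safety conclusion: a report built on these shells could not state how many subjects crossed the trial's own ECG limits, including whether that number was zero.

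**Working it through.** There is no stated figure to reproduce. The check sets each protocol limit against every visible safety table (14.3.1 to 14.3.6) and listing (16.2.3.1 to 16.2.3.12).

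**1. ECG limits**

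| Protocol 8.3 limit | Value or count in a table | Value in a listing |
|---|---|---|
| QTcF rise > 60 ms from Visit 1 | none | none |
| New QRS > 120 ms | none | none |
| PR > 240 msec, clinically significant | none; may fall in the abnormal, clinically significant category with all other causes | none; free text if abnormal |

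Result: 0 of 3 limits can be counted from interval values. Table 14.3.3 also takes each subject's worst post-baseline reading, so it is not a by-visit summary even of the categories.

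**2. Illustration for QTcF.** Take 370 ms at Visit 1 and 432 ms later. The change is 432 − 370 = 62 ms, above 60. The value is still below 450 ms, the male entry limit in exclusion criterion 16. That the evaluator would call this tracing normal is an assumption. The documents give no reading range for QTcF, and nothing in them prevents that reading.

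**3. What a count would be worth.** Assume all 24 planned subjects (protocol 7.2) have a post-baseline ECG. With zero cases, the upper 95% bound on the true rate is:
- one-sided: 1 − 0.05^(1/24) = 11.7%;
- two-sided exact: 1 − 0.025^(1/24) = 14.2%.

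For the 12 subjects of one sex the bounds are 22.1% and 26.5%. For assumed true rates of 2%, 5% and 10%, the chance of at least one case in 24, 1 − (1 − p)^24, is 38%, 71% and 92%. A zero count would be weak but reportable evidence; the present shells do not give the count.

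**4. Laboratory hold limits (Table 4, seven rows)**
- Counted in a table at the exact limit: 1 of 7 (AST/ALT > 3 x ULN, Table 14.3.5).
- Counted at a different limit: 1 of 7 (creatinine, > 1.5 x ULN against a hold limit of > 2 x ULN).
- Not counted in a table: 5 of 7 (the blood counts).
- Flagged per subject in a listing: 7 of 7 (five in 16.2.3.9, two in 16.2.3.10).

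**5. The reference.** Protocol Section 10 deals with study drug materials, and its headings run from 10.1 to 10.4. There is no 10.2.4.1. The hold criteria are in 9.9, Table 4.

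**The case against.** **The protocol's ECG-specific text is modest.** Section 13.4 says only that ECG results will be tabulated, and 12.1.4 defines the evaluator's result as normal or abnormal. On that reading Table 14.3.3 delivers what was promised. This has some force, but 13.1 covers all safety parameters by visit, and 8.3 itself treats QTcF, QRS and PR as safety parameters with limits. A worst-case category shift does not meet that.

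**The PR rule is not purely numeric.** It requires clinical significance, and the SAP has a category and a free-text field for that. This stands for PR in part: a flagged case could be found in the listing. It does not help for QTcF.

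**Interruptions and withdrawals are recorded elsewhere.** The adverse event, application-change and disposition listings show action taken. That is true, but only for recognized cases.

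**The laboratory side.** A reader might infer that the trial also cannot show who met the laboratory hold limits, or that blood counts are reported as means alone. The documents do not support either. The hold-criterion column in Listings 16.2.3.9 and 16.2.3.10 lets about 24 subjects be counted by hand, and the listed values allow the 8.3 blood-count limits to be checked too. Tables 14.3.4.1 and 14.3.4.2 follow the vital-signs format, which includes median, minimum and maximum of value and change, so an extreme count at a tabulated visit would be visible. Creatinine is a hold limit only, not an 8.3 discontinuation rule. Every subject above 2 x ULN is already inside the > 1.5 x ULN count, which bounds the number from above.

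**Conclusion.** The ECG point holds. None of the three interval-based withdrawal limits can be checked from the planned output independently of what sites flagged, and the SAP falls short of the by-visit summary in protocol 13.1. The gap is widest for QTcF, where the rule is a change that no planned table or listing records. It should be fixed because it bears on the safety part of the primary objective; it does not touch the efficacy analysis.

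The laboratory point is secondary and concerns presentation. Hold limits are flagged per subject, but six of seven are not counted in a table at the Table 4 limit. The wrong section reference is a real but minor error; the mock row already prints Table 4's hemoglobin criterion, so the intended source is clear.

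Two conditions apply. The SAP text ahead of the list of 14.3 tables was not available for this check, so any provision for ECG intervals there was not seen; the visible table and listing indexes contain none. The documents also do not say whether interval values are transferred to the analysis database.

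**What to change.** - **Listing 16.2.3.8:** add columns for QTcF, PR, QRS and heart rate, with QTcF change from Visit 1.
- **New table in the vital-signs format:** value and change by visit for the same parameters at the scheduled ECG visits (Visit 1, Weeks 4, 26 and 39, and follow-up or early termination). Add n (%) with a QTcF increase > 60 ms from Visit 1, n (%) with a new QRS > 120 ms, and n (%) with PR > 240 msec, showing how many of the last were judged clinically significant. Include unscheduled tracings in the counts, as Table 14.3.3 already does.
- **Laboratory, secondary:** add n (%) at each Table 4 hold limit as the protocol states it, including creatinine > 2 x ULN beside the existing > 1.5 x ULN row.
- **Reference:** change the programming note in Appendix 16.2.3.9 to protocol Section 9.9, Table 4.

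The ECG part costs one table shell, some listing columns and, if the values are not already in the database, a transfer of intervals from the central cardiology laboratory. The QTcF rule already requires those values to be known. The laboratory rows cost a short table from data already listed. No procedure, visit or clinical rule changes.

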Appendix 16.2.1.1 Disposition

Group: Female, Male

Patient	Date of Last Application ^a	Date of DC/ Completion	Days from Last Application ^b		Reason DC from Study	Period of Study Discontinuation/ Completion
xx-xxx	mmdddyy	mmdddyy	XX	xx	Adverse Event/SAE: list AE, link by AE number Protocol Violation Lost to Follow-Up Withdrew Consent Pregnancy Other: specify Completed	First 26 Weeks 6 Month Extension

^a Date of last dose of application of study medication.

NOTE: DC=Discontinued.

b DC date/Completion Date- date last application +1.

^c DC date/ Completion Date – date of first application of study medication +1.

23 Apr 2019 Statistical Analysis Plan

Protocol: ATI-50002-AGA-201

Appendix 16.2.1.2 Demographics

Patient	Age ^a (Years)	Gender	Race	Ethnicity	Fitzpatrick Skin Type	Height ^b (inches)	Weight ^l (lbs)
xx-xxx	XX	Male Female	Caucasian/White Black Asian/Oriental American Indian or Alaska Native Native Hawaiian or Pacific Islander Other - specify	Hispanic/Latino Not Hispanic/Latino Not Willing to Provide	1,2,3,4,5,6	xx.x	xxx xxx.x

^a At Date of signed informed consent.

^b FromV-2 Day 1 vitals page.

23 Apr 2019 Statistical Analysis Plan Protocol: ATI-50002-AGA-201

Appendix 16.2.1.3 History of Androgenetic Alopecia: Diagnosis and Prior Treatment and Therapies

Group: Female, Male

Patient	Onset Date of Diagnosis	Years Since Diagnosis ^a	Prior Treatment/ Therapy Type	Treatment or Therapy Coded/Verbatim	Start Date/ Stop Date	Start Day ^b / Stop Day ^b
xx-xxx	ddmmmyyyy	XX.X	Pharmaceutical	Minoxidil/	01Jan2018	55
				Rogaine/	03Jan2018	57
			Pharmaceutical	Finasteride/	01Jan2018	55
				Propecia	03Jan2018	57
			Device	Coded term/ verbatim		
			Other	Coded term/ verbatim		

NOTE: Date of Diagnosis from medical history page of CRF

PROGRAMMING NOTE: Will need to review prior treatment and therapies to assign "Type" i.e. "Pharmaceutical", "Device" and "other"

^a (Date of Diagnosis - Date of first application of study medication) / 365.

^b Start date – date of first application of study medication

23 Apr 2019 Statistical Analysis Plan

Protocol: ATI-50002-AGA-201

Appendix 16.2.1.4 Medical History

Group: Female, Male

Patient	Body System	Diagnosis	Onset Date (Study Day ^a)	Resolution Date (Study Day ^a)	Ongoing at Time of Randomization?
xx-xxx	Skin	Free Text	ddmmmyyyy (xx)	ddmmmyyyy (xx)	Yes
	Central nervous system		,		
	Ophthalmologic				
	Ear, nose, throat				
	Respiratory				
	Gastrointestinal				
	Hepatic				
	Renal				
	Cardiovascular				
	Hematologic				
	Genitourinary				
	Endocrine/Lymphatic Musculoskeletal				
	Systemic Infection				
	Drug Allergy				
	Substance Abuse				
	Psychiatric Psychiatric				
	Other				

^a Study Day = Start/stop date - date of first application of study medication.

PROGRAMMING NOTE: List dates as entered - i.e., display partial dates. Imputed dates in database are used to calculate study day. If patient has no entries, put "None" under Body System.

23 Apr 2019 Statistical Analysis Plan

Protocol: ATI-50002-AGA-201

Appendix 16.2.1.5 Prior and Concomitant Therapies

Group: Female, Male

Patient	WHO ATC Level III/ WHO Preferred Term/ Verbatim Term	Dose (unit) [Route] Frequency	Study Period(s) in Which Received ^a		Start Day ^b / Stop Day ^b	Indication	Associated with AE (AE#)
		xx (mg) [oral] QD	P O F P,O O,F P,O,F	01Jan2018 03Jan2018		Free Text	No Yes (xx)
			1,0,1	Note: if "ongoing", put "ongoing" under Stop Date			

NOTE: -= data not available

^a P = Prior medication; O = Treatment Period; F=Post-Therapy

b Start date – date of first application of study medication (+1 if ≥ first application of study medication).

23 Apr 2019 Statistical Analysis Plan

Protocol: ATI-50002-AGA-201

Appendix 16.2.1.6 ATI-50002 Accountability

			Dispensed					V	olume
Patient	Date Dispensed	Study Day ^a Dispensed	Bottle Weight Date (gm) Collected		Study Day ^a Collected	Collected Bottle Weight (gm)	Amount - Used ^b (gm)	(mL) ^c	Volume (mL) Per Application ^c
xx-xxx	ddmmmyyyy	XX	XX	ddmmmyyyy	XX	XX	XX	XX	
	ddmmmyyyy		XX	ddmmmyyyy	XX	XX	XX	XX	
	ddmmmyyyy	XX	XX	ddmmmyyyy	XX	XX	XX	XX	
	ddmmmyyyy	XX	XX	ddmmmyyyy	XX	XX	XX	XX	
	ddmmmyyyy	XX	XX	ddmmmyyyy	XX	XX	XX	XX	
	ddmmmyyyy	XX	XX	ddmmmyyyy	XX	XX	XX	XX	
						TOTAL:	XX	XXX	XX.X

^a Dispensed Date (or Collection Date) – Date first Application +1.

^b Weight dispensed – Weight collected (returned).

^c The density of study agent is 1 g/mL which is used to convert differences in bottle weights between dispensed and returned (ie weight of study agent used) to mLs.

23 Apr 2019 Statistical Analysis Plan

Protocol: ATI-50002-AGA-201

Appendix 16.2.1.7 ATI-50002 Accountability Comments

	Date	Study Day ^a Dispensed	Date	Study Day ^a	
Patient	Dispensed		Collected	Collected	Comment
xx-xxx	ddmmmyyyy	XX	ddmmmyyyy	XX	Free Text
	ddmmmyyyy	XX	ddmmmyyyy	XX	
	ddmmmyyyy	XX	ddmmmyyyy	XX	
	ddmmmyyyy	XX	ddmmmyyyy	XX	
	ddmmmyyyy	XX	ddmmmyyyy	XX	
	ddmmmyyyy	XX	ddmmmyyyy	XX	
	ddmmmyyyy	XX	ddmmmyyyy	XX	
	ddmmmyyyy	XX	ddmmmyyyy	XX	
	ddmmmyyyy	XX	ddmmmyyyy	XX	

^a Dispensed Date (or Collection Date) – Date first Application +1.

23 Apr 2019 Statistical Analysis Plan

Protocol: ATI-50002-AGA-201

